12.6 Appendix: Modified Cumulative Illness Rating Scale - Geriatric

MODIFIED CUMULATIVE ILLNESS RATING SCALE (CIRS-G)		
Each system is rated as follows:		
0 =	NONE: No impairment to that organ/system	
1 =	MILD: Impairment does not interfere with normal activity; treatment may or may not be required; Prognosis is excellent. (Examples could be skin lesions, hernias, or hemorrhoids)	
2 =	Moderate: Impairment interferes with normal activity; treatment is needed; prognosis is good. (Examples could be gallstones, diabetes, or fractures)	
3 =	SEVERE: Impairment is disabling; treatment is urgently needed; prognosis is guarded. (Examples could be resectable carcinoma, pulmonary emphysema, or congestive heart failure)	
4 =	EXTREMELY SEVERE: Impairment is life threatening; treatment is urgent or of no avail; prognosis is grave. (Examples could be myocardial infarction, cerebrovascular accident, gastrointestinal bleeding, or embolus).	
Sr. No.	System	Rating (0-4)
1.	Cardiac (heart only)	
2.	Hypertension (rating is based on severity; affected systems are rated separately)	
3.	Vascular (blood, blood vessels and cells, marrow, spleen, lymphatics)	
4.	Respiratory (lungs, bronchi, trachea below the larynx)	
5.	EENT (eye, ear, nose, throat, larynx)	
6.	Upper GI (esophagus, stomach, duodenum, biliary and pancreatic trees; do not include diabetes)	
7.	Lower GI (intestines, hernias)	
8.	Hepatic (liver only)	
9.	Renal (kidneys only)	
10.	Other GU (ureters, bladder, urethra, prostate, genitals)	
11.	Musculo-Skeletal-Integumentary (muscles, bone, skin)	
12.	Neurological (brain, spinal cord, nerves; do not include dementia)	
13.	Endocrine-Metabolic (includes diabetes, diffuse infections, infections, toxicity)	
14.	Psychiatric/Behavioral (includes dementia, depression, anxiety, agitation, psychosis)	
How many Ratings of 2 : _____		How many Ratings of 3-4 : _____

Reference: Based on Parmelee et al. *J Am Geriatr Soc* 1995

SoC	standard of care
SoE	schedule of events
TEAE	treatment-emergent adverse event

1 Introduction

This statistical analysis plan (SAP) describes the statistical methods to be used during the reporting and analysis of data collected under ADC Therapeutics Protocol ADCT-402-203. The company decided to discontinue the study on 20 Jul 2023. Given the challenges of defining the addressable segment of this difficult-to-treat patient population, the benefit-risk profile does not support continuation of the LOTIS-9 trial. So not all the analyses specified in study protocol are covered by the SAP. Analyse of PK/Biomarker data will be covered in separate SAP if needed.

This SAP should be read in conjunction with the study protocol and case report form (CRF). This version of the plan has been developed using the Protocol Amendment 3 08 August 2022 and CRF version dated 02 Feb 2023.

2 Study Objectives

2.1 Primary Objectives

Cohort A

- To assess the efficacy of a response-adapted treatment of Lonca-R in unfit patients with previously untreated DLBC, or HGBCL, or Grade 3b FL

Cohort B

[figure not shown]
- To assess the tolerability and efficacy of a response-adapted treatment of Lonca-R in frail patients or patients with cardiac comorbidities with previously untreated DLBCL who are ineligible for standard R-mini-CHOP

2.2 Secondary Objectives

Cohort A and Cohort B

- Further evaluate the efficacy of Lonca-R
- To characterize the safety profile of Lonca-R
- To characterize the PK profile of Lonca when given in combination with rituximab
- To evaluate the immunogenicity of Lonca when given in combination with rituximab
- To evaluate the impact of Lonca-R treatment on treatment-related and disease-related symptoms, patient-reported functions, and overall health status

Due to early termination of the study, patients are not followed up for sufficient time. Some endpoints for secondary objectives, such as progression-free survival (PFS), overall survival (OS) and patient reported outcome (PRO), will not be analyzed because of lack of sufficient follow up.

[figure not shown]
3 Study Design

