Physical examination	7.4.1	X	X		X	X	X		X	X
Vital signs ⁴	7.4.4	X	X	X	X	X	X		X	X
12-lead ECG	7.4.7	X								
Height	7.4.3	X								
Weight	7.4.3	X	X		X	X	X		X	X
ECOG PS	7.4.2	X	X			X	X			X
CCI										

	Protocol Section	Screening	Treatment Period								Follow-up Period (up to 5 years from EoT)
1 cycle = 21 days			Cycle 1			Cycle 2	Cycle 3		Cycle 4-6	EoT ²	
		Day - 28 to Day -1	Day 1	Day 2 (+2 days)	Day 9 (±2 days)	Day 1 (±2 days)	Day 1 (±2 days)	Day 15 (±2 days)	Day 1 (±2 days)		
Disease assessment	7.3	X ⁶						X ⁶	X (end of C6 only)	X ⁶	X Every 12 weeks until 1 year, then every 24 weeks for 2 years then annually
Hematology and Chemistry ⁷	7.4.5	X	X	X	X	X	X		X	X	
HIV, HBV, HCV status	7.4.5	X									
Urinalysis	7.4.5	X	X							X	
Pregnancy test ⁸	7.4.6	X	X				X			X	X
LVEF (Echo/MUGA)	5.1	X								X	
PK sample ⁹	7.5.1			X (pre-dose, Lonca EOI)		X (pre-dose, Lonca EOI)	X (pre-dose, Lonca EOI)		X (pre-dose, Lonca EOI)	X	
ADA sample ¹⁰	7.5.2			X (pre-dose)		X (pre-dose)			X (C4 and C6 only; pre-dose)	X	

	Protocol Section	Screening	Treatment Period							Follow-up Period (up to 5 years from EoT)	
			Cycle 1			Cycle 2	Cycle 3		Cycle 4-6		
1 cycle = 21 days		Day - 28 to Day -1	Day 1	Day 2 (+2 days)	Day 9 (±2 days)	Day 1 (±2 days)	Day 1 (±2 days)	Day 15 (±2 days)	Day 1 (±2 days)	EoT ²	
CCI											
CCI											
Patient Reported Outcomes Assessment ¹²	7.6		X ¹²			X ¹²	X ¹²		X ¹²	X ¹²	
Optional Pre-Phase Therapy	4.2.1	X									
Lonca-R ¹³											
Premedication ¹⁴	6.4		X			X	X ¹⁴		X ¹⁴		
Rituximab administration	6.3		X			X	X ¹³		X ¹³		
Loncastuximab tesirine administration	6.3			X		X	X ¹³		X ¹³		
Concomitant medications	6.9	From ICF signature date or D-14, whichever is earlier, until 30 days after last dose of study treatment and as indicated for AE/SAEs thereafter.									
AEs	8	All AE/SAEs, regardless of the relationship to study treatment, will be reported from ICF signature date until 15 weeks after last dose of study treatment or the start of new anti-cancer therapy, whichever is earlier; thereafter, only related SAEs will be reported.									
Survival information										X	X

	Protocol Section	Screening	Treatment Period							Follow-up Period (up to 5 years from EoT)
			Cycle 1			Cycle 2		Cycle 3		
1 cycle = 21 days										EoT ²
		Day - 28 to Day -1	Day 1	Day 2 (+2 days)	Day 9 (±2 days)	Day 1 (±2 days)	Day 1 (±2 days)	Day 15 (±2 days)	Day 1 (±2 days)	
First new anticancer treatment information										X X

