Cohort A and Cohort B: 
• Further evaluate the efficacy of Lonca-R• To characterize the safety profile of Lonca-R• To characterize the PK profile of Lonca when given in combination with rituximab• To evaluate the immunogenicity of Lonca when given in combination with rituximab• To evaluate the impact of Lonca-R treatment on treatment-related and disease-related symptoms, patient-reported functions, and overall health status	Cohort A and Cohort B: 
• ORR according to the 2014 Lugano Classification, defined as the proportion of patients with a BOR of CR or PR.• 2-year PFS, defined as the proportion of patients that are PFS event-free at 2 years.• 3-yr OS, defined as the proportion of patients that are OS event-free at 3 years.• DoR defined as the time from the first documentation of tumor response (CR or PR) to disease progression or death• Frequency and severity of AEs and SAEs.

Objectives	Endpoints
	
• Changes from baseline in safety laboratory variables, vital signs, physical examinations, ECOG PS• Concentrations and PK parameters of loncastuximab tesirine PBD-conjugated antibody, total antibody, and SG3199 unconjugated warhead• Frequency of confirmed positive ADA responses, their associated titers and, if applicable, neutralizing activity to loncastuximab tesirine after treatment with loncastuximab tesirine when given in combination with rituximab• Changes in patient-reported outcomes (e.g., symptoms, functions, and overall health status) from baseline as evaluated by FACT-Lym
Exploratory	
CCI	CCI

Abbreviations: ADA, anti-drug antibody; AE, adverse event; BOR, best overall response; CR, complete response; DLBCL, diffuse large B-cell lymphoma; DoR, duration of response; EoT, end of treatment; ECOG PS, Eastern Cooperative Oncology Group scale of performance status; FACT-Lym, Functional Assessment of Cancer Therapy-Lymphoma; Lonca-R, loncastuximab tesirine and rituximab; ORR, overall response rate; OS, overall survival; PBD, pyrrolobenzodiazepine; PFS, progression free survival; PK, pharmacokinetic; PR, partial response; PS, performance status; R-CHOP, combination of rituximab, cyclophosphamide, doxorubicin, vincristine, and prednisone, SAE, serious adverse event.

4 Study Design

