5.5.2 Discontinuation from the Study

A patient may be discontinued from the study for any of the following reasons:

- Study completion
- Withdrawal of consent
- Investigator decision
- Lost to follow-up
- Study termination by the Sponsor
- Death
- Other

If a patient withdraws informed consent for study participation, no additional study data will be collected.

The Sponsor may continue to use previously collected medical research data prior to the withdrawal consistent with the original authorization. If a patient withdraws from the study, he/she may request destruction of any samples taken and not tested, and the investigator must document this in the site study records.

The study may be terminated at any time, for any reason, by the Sponsor. Patients still receiving study drug will have an EoT visit as described in [Section 4.2.3](#) and schedule of events (SoE) ([Table 2](#)).

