9.12 Patient-reported Outcomes

Patient-reported outcomes will be analyzed among PRO population. Details will be provided in the SAP.

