4.1.2 Patient-reported Outcomes Population

All patients who receive at least one dose of study treatment and complete at least one questionnaire at baseline and at one post baseline visit.

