4.8 Efficacy Analyses

Efficacy analyses will be based on response as determined by investigator with the All-treated population. The endpoints for efficacy include Complete Response Rate (CRR), Overall Response Rate (ORR) according to the 2014 Lugano classification as determined by investigator (See Lugano classification in Appendix x), Duration of Response (DoR).

All efficacy endpoints and tumor assessment data will be listed in patient level.

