4.9.1.2 Deaths

The following deaths summaries will be generated on the all-treated population.

- Number (%) of patients who died during the study and reasons for death
- Number (%) of patients who died within 15 weeks after the last dose of study drug (excluding those who died after taking any subsequent anticancer therapy/procedure) and reasons for death

Listing of deaths will be provided.

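### The SAP's follow-up reason fits 2-year PFS and 3-year OS but not, by itself, FACT-Lym, whose schedule ends at EoT and which is left with no table or listing

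*SAP*

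**What the plan says.** - SAP 2.2 keeps the objective on symptoms, patient-reported function and overall health status. It then says that PFS, "overall survival (OS) and patient reported outcome (PRO), will not be analyzed because of lack of sufficient follow up".
- Protocol Table 3 makes FACT-Lym change from baseline a secondary endpoint in both cohorts. Protocol 9.12 adds: "Patient-reported outcomes will be analyzed among PRO population. Details will be provided in the SAP".
- In Protocol Table 2 the row "Patient Reported Outcomes Assessment" is marked on Day 1 of Cycles 1, 2, 3 and 4-6 and at EoT. Its follow-up column is empty, and Protocol 7.6 adds no other time point.
- Protocol 4.2.3 puts EoT 28 (±7) days after the last dose. On termination by the sponsor, Protocol 5.5.2 says: "Patients still receiving study drug will have an EoT visit as described in" the EoT section.
- SAP 4.1.2 defines a PRO Population of treated patients who "complete at least one questionnaire at baseline and at one post baseline visit". No later SAP section uses it.
- Listings are specified elsewhere. SAP 4.8 has "All efficacy endpoints and tumor assessment data will be listed in patient level", where the efficacy endpoints named are CRR, ORR and DoR. SAP 4.9.1.2 has "Listing of deaths will be provided".
- The PFS endpoint in Protocol Table 3 is a landmark: "2-year PFS, defined as the proportion of patients that are PFS event-free at 2 years". OS is treated the same way at 3 years.
- SAP 3.4, the section for changes to the protocol's statistical section, is marked not applicable.

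**The concern.** One reason is applied to endpoints with very different time needs. The survival landmarks need years of observation, whereas FACT-Lym needs only the treatment period and one visit about four weeks after the last dose. A shortage of long-term follow-up therefore does not explain why the questionnaire is left out.

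The trial was stopped because the benefit-risk profile in unfit and frail patients did not support continuing. How treatment affected symptoms and function is a stated secondary objective, and under the current SAP the patients' own answers would not appear even as a listing.

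The record of changes is also incomplete. SAP 2.2 introduces the dropped endpoints as examples, so the list stays open, and SAP 3.4 records no change. A reader cannot tell which other protocol analyses were left out on purpose. For instance, SAP 4.8 has no analysis of the Cohort B tolerability proportion, and the subgroup analyses of Protocol 9.11 are absent.

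**Working it through.** The plan gives no figure for follow-up achieved or questionnaires completed, so there is none to reproduce. The check compares the time each endpoint needs with the time available.

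**1. Landmarks.** The original protocol is dated 01 Nov 2021 (protocol version list) and the stop decision 20 Jul 2023 (SAP 1). The difference is 365 + 261 = 626 days. No patient can have been followed longer than this by the decision date. Two years is 730 days and three years is 1,095, so neither landmark was reachable by then. The data cut-off is not given.

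**2. FACT-Lym.** Cycles last 21 days. Without dose delays, EoT falls 21 × (cycles − 1) + 28 days after C1D1, ±7:

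| Cycles given | EoT, days after C1D1 | With window | Questionnaires |
|---|---|---|---|
| 3 | 42 + 28 = 70 | 63-77 | 4 |
| 4 | 63 + 28 = 91 | 84-98 | 5 |
| 6 | 105 + 28 = 133 | 126-140 | 7 |

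Patients who stop before Cycle 3 finish sooner. Counting back from 20 Jul 2023 with the latest window, a patient starting by 02 Mar 2023 (140 days) could complete a 6-cycle schedule, and one starting by 13 Apr 2023 (98 days) a 4-cycle schedule. Enrolment dates are not given, so the number of such patients among the 41 treated is unknown.

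**3. Outputs.** The SAP tabulates or lists response, DoR, deaths, adverse events, laboratory data, ECG, vital signs and ECOG PS. It also lists physical examinations and pregnancy tests. FACT-Lym appears in none of these outputs.

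**4. Scoring.** A restored table needs a scoring rule, because Protocol 7.6 says that a higher score means worse quality of life. Appendix 12.3 has 7 + 7 + 6 + 7 + 15 = 42 items, each scored 0-4. By their wording, 7 social + 1 emotional + 7 functional = 15 are positive, and 7 physical + 5 emotional + 15 additional = 27 are negative. The raw sums are:
- best state: 15 × 4 + 27 × 0 = 60
- worst state: 15 × 0 + 27 × 4 = 108
- every item at 4: 42 × 4 = 168

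The highest raw sum is not the worst state, so the items must be recoded to one direction. Item GS7 may be skipped by choice, and the SAP's missing-data section has no rule for an unanswered item.

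**5. Precision (assumed counts).** The 95% half-width of a mean paired change, in SD of change, is t(0.975, n−1)/√n. For 10 pairs in a cohort it is 0.72, and for 20 pairs 0.47. The cohort split is not given.

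**6. Time-to-event coverage.** DoR is defined for CR or PR patients only. If ORR were 60%, 73% or 90% (assumed), responders would number about 25, 30 or 37, and the curve would leave out 16, 11 or 4 of the 41 patients.

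**The case against.** **PFS and OS.** A reader might infer that dropping these is equally unjustified. The documents do not support that. The protocol's endpoints are the 2-year and 3-year proportions, neither could be reached by the stop decision, and the protocol names no curve without a landmark as an endpoint. Tumor assessments, deaths and subsequent therapies are still listed, and deaths are counted in all treated patients. Curves without a landmark would be an optional addition.

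**Meaning of follow-up.** SAP 2.2 may mean more than the post-treatment period and may include treatment schedules cut short by termination. An EoT visit does not replace missed cycle visits. This stands in part. A reader might infer that a usable PRO data set was thrown away, but with no enrolment dates or completion counts the documents cannot show that. They show only that the reason given is not enough for this endpoint.

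**Disclosure.** A reader might infer that the omission is hidden. It is not: SAP 1 says some protocol analyses are not covered, and SAP 2.2 names PFS, OS and PRO. The fault lies in the open-ended list and the entry in SAP 3.4.

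**Other data.** Function and toxicity are not wholly unreported, since ECOG PS by visit and graded adverse events are summarised. Those are clinician-recorded and do not answer the patient-reported objective.

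**Dropout.** Patients who progress, suffer toxicity or die stop contributing, so later means describe a selected group. This stands, and it limits any FACT-Lym table to description.

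**Conclusion.** The point holds for FACT-Lym. Its last scheduled questionnaire falls nominally 70, 91 or 133 days after C1D1, against the 730 and 1,095 days that make the follow-up reason valid for PFS and OS. The SAP defines a population for it and then reports nothing from it. The primary CRR analysis is unaffected.

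This rests on reading the follow-up cell of the PRO row in Table 2 as blank, which agrees with the column positions of neighbouring rows, and on nominal timing without dose delays. It does not establish how many questionnaires exist or that a table would be informative. If few were completed, that would be a sound reason for having no table, but it is not the reason the SAP gives and it would not rule out a listing.

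**What to change.** 1. **FACT-Lym.** Add a descriptive change from baseline by cycle and at EoT, by cohort, in the PRO Population, with completed and expected questionnaires per visit and a patient-level listing. Recode the items to one stated direction, replace the direction sentence in Protocol 7.6, and say how unanswered items, including GS7, are handled. If there are too few questionnaires for a table, give the count as PRO's own reason and still list the scores.
2. **SAP 3.4.** Replace the present entry with each protocol analysis dropped or changed, and the reason for each.
3. **Optional.** Add descriptive Kaplan-Meier PFS and OS by cohort in the All-Treated Population, with numbers at risk and no 2-year or 3-year claim. Time should run from first dose, because Protocol 9.7.5 starts OS at randomization and SAP 3.3 says there is none. Without these curves, DoR is the only time-to-event summary and covers responders only.

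The cost is SAP text, one table and one listing from data already scheduled for collection, plus two curves per cohort if the option is taken. The downside is small cohorts and selective dropout, so all of it must be labelled descriptive.

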3.1 Overview

This is a Phase 2, multicenter, multi-cohort, open-label study of Lonca-R in unfit/frail patients with previously untreated DLBCL. Fitness and frailty of the patients will be assessed using the sGA tool developed by the FIL. A response-adapted approach will be used in this study. Two parallel cohorts will enroll patients; Cohort A will enroll unfit patients and Cohort B will enroll frail patients or patients with cardiac comorbidities (Figure 1).

A treatment cycle in the study is defined as 3 weeks (i.e., 21 days). Cohort A will assess efficacy and Cohort B will assess the efficacy and tolerability of Lonca-R. After completion of 3 cycles of Lonca-R treatment, patients who achieve CR or PR will continue to receive 1 additional cycle or 3 cycles of Lonca-R, respectively. Patients in Cohort A who do not achieve a CR or PR will discontinue study treatment. For Cohort B only, patients who achieve stable disease (SD) and derive clinical benefit per the treating physician may continue to receive additional 3 cycles of Lonca-R.

Eligible patients will be administered through IV with loncastuximab tesirine 150mcg/kg for the first 2 cycles starting at C1D2. For subsequent cycles, the dose level will be reduced to 75mg/kg. Rituximab will be dosed through IV with dose level of 375 mg/m² starting at C1D1.

Abbreviations: CR, complete response; Lonca-R, loncastuximab tesirine in combination with rituximab; PET-CT, positron emission tomography-computed tomography; PR, partial response; SD, stable disease; sGA, simplified geriatric assessment.

3.2 Sample Size Consideration

A sample size of 40 patients for each cohort is considered adequate to assess safety and efficacy in the corresponding study population. The percentage of ORR and CR rate with its 95% CI will be presented

descriptively. The primary endpoint, CRR, will be calculated based on the exact Clopper-Pearson Method.

Number of Patients	Number of CRs	CRR	Confidence intervals based on exact Clopper-Pearson method		
			90% CI for CRR	95% CI for CRR	99% CI for CRR
40	12	30%	(18.3, 44.0)	(16.6, 46.5)	(13.4, 51.4)
40	16	40%	(26.9, 54.2)	(24.9, 56.7)	(21.0, 61.4)
40	20	50%	(36.1, 63.9)	(33.8, 66.2)	(29.5, 70.5)
40	24	60%	(45.8, 73.1)	(43.3, 75.1)	(38.6, 79.0)

As of 20 Jul 2023 when decision was made to discontinue the study, 41 patients were enrolled and treated in total.

3.3 Randomization

Not applicable.

3.4 Modifications to the statistical section of the protocol

Not applicable

4 Statistical Methods

All analyses will use SAS® version 9.4 or higher.

Categorical data will be presented using counts and percentages, with the number of patients in the analysis population as the denominator for percentages. Percentages will be rounded to 1 decimal place and not be displayed for zero counts.

Continuous data will be summarized using the number of observations (n), mean, standard deviation (std), median, minimum, and maximum. Minima and maxima will be rounded to the precision of the original value, and means, medians, and 95% confidence intervals (CIs) if presented will be rounded to 1 decimal place greater than the precision of the original value. The std will be rounded to 2 decimal places greater than the precision of the original value, up to a maximum of 3 decimal places.

4.1 Analysis Populations

4.1.1 All-Treated Population

All patients who receive at least 1 dose of study drug. This population will be used in the primary analyses of efficacy and safety for both cohorts.

4.1.2 Patient-reported Outcomes Population

All patients who receive at least one dose of study treatment and complete at least one questionnaire at baseline and at one post baseline visit.

4.1.3 PK Population

All patients who receive study drug and have at least 1 pre- (C1D1) and 1 post-dose valid PK assessment.

4.1.4 Immunogenicity Population

All patients who receive study drug and have at least 1 valid anti-drug antibody assessment.

4.2 Patient Disposition

The number and percentage of patients enrolled and treated in the study will be presented. In addition, the number and percentage of patients who withdrew from study treatment and who discontinued the study for each reason will be tabulated..

Patient disposition data will be listed in patient level.

